10. STATISTICAL METHODS

10.1. Primary endpoints

- Occurrence of AEs from vaccination up to Day 7, for all subjects in each investigational RSV vaccine group:
 - Occurrence of any Grade 2 and Grade 3 general AE (solicited and unsolicited);
 - Occurrence of Grade 2 and Grade 3 fever;
 - Occurrence of any vaccine-related SAE.
- Functional antibody titres against RSV at Day 0 and Day 30, for all subjects in each investigational RSV vaccine group.
 - Neutralising antibody titres against RSV-A .
- PCA concentrations at Day 0 and Day 30 for all subjects in each investigational RSV vaccine group.

10.2. Secondary endpoints

- Occurrence of AEs from vaccination up to study conclusion:
 - Occurrence of each solicited local and general AE, during a 7-day follow-up period after vaccination (i.e. the day of vaccination and 6 subsequent days), for all subjects in all groups;
 - Occurrence of any unsolicited AE, during a 30-day follow-up period after vaccination (i.e. the day of vaccination and 29 subsequent days), for all subjects in all groups;
 - Occurrence of any haematological (haemoglobin level, White Blood Cells [WBC], lymphocyte, neutrophil, eosinophil and platelet count) and biochemical

(alanine amino-transferase [ALT], aspartate amino-transferase [AST] and creatinine) laboratory abnormality at Day 0, Day 7, Day 30, Day 60 and Day 90 for all subjects in all groups;

- Occurrence of any SAE, for all subjects in all groups.
- Functional antibody titres against RSV for all subjects in all groups:
 - Neutralising antibody titres against RSV-A at Day 0, Day 30, Day 60 and Day 90;
 - Neutralising antibody titres against RSV-B at Day 0, Day 30, Day 60 and Day 90.
- PCA concentration at Day 0, Day 30, Day 60 and Day 90 for all subjects in all groups.
- Humoral immune response to the residual host cell protein NEO in the investigational RSV vaccine at pre-vaccination (Day 0), and 1 month post-vaccination (Day 30) for all subjects in all groups.
 - Neutralising antibody titres against NEO
- Occurrence of medically attended RSV-associated RTIs up to study conclusion.

10.3. Tertiary endpoints

See section 5.7.3 for additional testing proposed to further characterise the immune response to the investigational RSV vaccine.

10.4. Determination of sample size

The main objective of the study is to rank different formulations of the investigational RSV vaccine based on immunogenicity and safety/reactogenicity data up to 1 month post-vaccination (Day 30).

The sample size was determined to allow reliable ranking of the investigational RSV vaccine formulations based on a desirability index (see details in [APPENDIX E](#)) combining the following endpoints:

- Incidence rate of any Grade 2 and any Grade 3 general AE (solicited and unsolicited) and any vaccine-related SAE during the 7-day follow-up period after vaccination for each investigational RSV vaccine formulation.
- Incidence rate of Grade 2 and Grade 3 fever during the 7-day follow-up period after vaccination for each investigational RSV vaccine formulation.
- Neutralising antibody titres against RSV-A at 1 month post-vaccination.
- PCA concentrations at 1 month post-vaccination.

Different plausible scenarios (2 for immunogenicity and 2 for reactogenicity) were simulated several times and the desirability analysis for formulation selection was applied on each simulated data package, as described below.

Immunogenicity

1. The functional antibody response covers a range from 10 log₂ (30 PreF) to 12 log₂ (120 PreF) for neutralising RSV-A titres, and from 100 to 200 for the PCA concentrations.
2. The functional antibody response covers a range from 10 log₂ (30 PreF) to 11 log₂ (120 PreF) for neutralising RSV-A titres, and from 100 to 150 for the PCA concentrations.

Reactogenicity

1. The incidence rate varies between 25% (30 PreF) and 30% (120 PreF) for the Grade 2/3 general AEs, and between 2% and 4% for Grade 2/3 fever.
2. The incidence rate varies between 25% (30 PreF) and 50% (120 PreF) for the Grade 2/3 general AEs, and between 4% and 10% for Grade 2/3 fever.

These four combinations of scenarios were simulated 10000 times in SAS, with a sample size of 95 evaluable subjects per group (see details in [APPENDIX E](#)). The percentages for ranking each formulation at the first place and for selecting the best formulation were computed.

Simulations in SAS shows that a sample size of 100 subjects enrolled per group (N=95 evaluable subjects) allows to reach a percentage >80% for selecting one of the best formulations, i.e. with a high immune response and acceptable reactogenicity. Moreover, this sample size will allow to have a small percentage (<5%) for selecting formulations with an unacceptable reactogenicity.

10.5. Cohorts for Analyses

Two cohorts will be defined for the purpose of the analysis: the Total Vaccinated Cohort (TVC) and the ATP cohort for analysis of immunogenicity. All analyses will be performed per treatment actually administered.

10.5.1. Total vaccinated cohort

The TVC will include all subjects with study vaccine administration documented:

- A safety analysis based on the TVC will include all vaccinated subjects
- An immunogenicity analysis based on the TVC will include all vaccinated subjects for whom immunogenicity data are available.

10.5.2. According-to-protocol cohort for analysis of immunogenicity

The ATP cohort for immunogenicity will be defined by time point and will include all vaccinated subjects:

- Meeting all eligibility criteria (i.e. no protocol violation linked to the inclusion/exclusion criteria, including age).

- Who received the study vaccine according to protocol procedures.
- Who did not receive a concomitant vaccination/medication/product leading to exclusion from an ATP analysis up to the corresponding timepoint as described in Section 6.6.2.
- Who did not present with an intercurrent medical condition leading to exclusion from an ATP analysis up to the corresponding timepoint, as described in Section 6.7.
- Who complied with the post-vaccination blood sampling schedule at the corresponding timepoint, as specified in Table 5.
- For whom post-vaccination immunogenicity results are available for at least 1 assay at the corresponding timepoint.

When presenting different timepoints, the ATP cohort for immunogenicity will be adapted for each timepoint (up to D30 and up to D90).

10.6. Derived and transformed data

The study groups will be defined by treatment actually administered.

Demography

- For a given subject and a given demographic variable, missing measurements will not be replaced.

Safety

- For a given subject and the analysis of solicited symptoms during the 7-day follow-up period after vaccination, missing or non-evaluable measurements will not be replaced. Therefore the analysis of the solicited symptoms based on the TVC will include only vaccinated subjects with documented safety data (i.e., symptom screen completed).
- For analysis of unsolicited AEs, SAEs and for the analysis of concomitant medications, all vaccinated subjects will be considered. Subjects who did not report an event or concomitant medication will be considered as subjects without the event or the concomitant medication respectively.

Immunogenicity

- Any missing or non-evaluable immunogenicity measurement will not be replaced:
 - For the within-group assessment, the descriptive analysis performed for each assay at each timepoint will exclude subjects with a missing or non-evaluable measurement.
 - For the between group assessments, the Analysis of covariance (ANCOVA) model will be fitted at each timepoint based on the subjects having a result at both the baseline and the considered timepoint.

- A seronegative subject will be defined as a subject whose antibody titre/concentration is below the cut-off value of the assay. A seropositive subject is a subject whose antibody titre/concentration is greater than or equal to the cut-off value of the assay.
- The geometric mean titres (GMTs)/geometric mean concentrations (GMCs) will be computed by taking the anti-logarithm of the arithmetic mean of the log₁₀ transformed titres/concentrations.
- Vaccine response in terms of RSV neutralising antibodies will be defined as:
 - At least a 4-fold increase from pre-vaccination if pre-vaccination neutralising antibody titre $< 7 \log_2$ (< 128).
 - At least a 3-fold increase from pre-vaccination if pre-vaccination neutralising antibody titre in $[7-8] \log_2$ ($[128-256]$).
 - At least a 2.5-fold increase from pre-vaccination if pre-vaccination neutralising antibody titre in $> 8-10 \log_2$ ($> 256-1024$).
 - At least 1-fold from pre-vaccination if pre-vaccination neutralising antibody titre $> 10 \log_2$ (> 1024).
- The handling of data below the assay LLOQs for GMT/GMC calculations and evaluation of vaccine response will be described in the SAP.

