1.2.3. Rationale for the use of placebo

The placebo group is included as a control for both the safety/reactogenicity and immunogenicity assessments.

[figure not shown]

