5.2.2.2.1. Study group and treatment number allocation

The target will be to enrol approximately 400 eligible subjects who will be randomly assigned to four study groups in a (1: 1: 1: 1) ratio (approximately 100 subjects in each group).

Allocation of the subject to a study group at the investigator site will be performed using SBIR. The randomisation algorithm will use a minimisation procedure accounting for age (18 - 32 years or 33 - 45 years) and centre. Minimisation factors will have equal weight in the minimisation algorithm.

After obtaining the signed and dated ICF from the subject and having checked the eligibility of the subject, the site staff in charge of the vaccine administration will access SBIR. Upon providing the subject identification number, the randomisation system will determine the study group and will provide the treatment number to be used for the first dose.

The number of each administered treatment must be recorded in the eCRF on the Vaccine Administration screen.

When SBIR is not available, please refer to the SBIR user guide or the Study Procedures Manual (SPM) for specific instructions.

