10.10. Analysis of immunogenicity

The analysis will be performed on the applicable ATP cohort for immunogenicity and, if in any group the percentage of vaccinated subjects with serological results excluded from the ATP cohort for analysis of immunogenicity is $\geq 5\%$, a second analysis will be performed on the TVC.

Within group evaluation

Humoral Immune response to RSV vaccine

For each group, at each timepoint that blood samples are collected and for each assay (unless specified otherwise):

- GMTs/GMCs will be tabulated with 95% CI and represented graphically.
- Percentage of subjects above the seropositivity threshold will be tabulated with exact 95% CI.
- Pre- and post-vaccination antibody titres/concentrations will be displayed using reverse cumulative curves.
- The distributions of **neutralising** antibody titres will be tabulated.
- Percentage of responders in terms of **neutralising** antibody titres will be tabulated with exact 95% CI.
- Individual post-vaccination *versus* pre-vaccination results will be plotted using scatter plots. Results of the control group will be used as a reference.
- Geometric mean of ratios of antibody titres/concentrations at each post-vaccination timepoint over pre-vaccination will be tabulated with 95% CI.
- Distribution of the fold increase of **neutralising** antibody titres will be tabulated: by pre-vaccination titre category: < 7 , $7-8$, $> 8-9$, $> 9-10$, $> 10-11$, $> 11-12$, $> 12 \log_2$, and by cumulative categories: < 7 , ≥ 7 , ≥ 8 , ≥ 9 , ≥ 10 , ≥ 11 , $\geq 12 \log_2$.
- The kinetics of individual antibody titres/concentrations will be plotted as a function of time for subjects with results available at all timepoints.
- An analysis of variance model for repeated measures will be fitted to assess the mean profile in each group.

If deemed necessary, the same analyses may be done by age category (18 - 32 years and 33 - 45 years).

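### Above a baseline of 10 log2, the vaccine-response rule read literally counts an unchanged titre as a response, which inflates the descriptive responder percentages

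*Protocol*

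**What the plan says.** Protocol Section 10.6 (Derived and transformed data, Immunogenicity) defines vaccine response for RSV neutralising antibodies by baseline tier:

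- below 7 log2 (128): "At least a 4-fold increase from pre-vaccination if pre-vaccination neutralising antibody titre" is in this tier;
- 7 to 8 log2 (128 to 256): "At least a 3-fold increase from pre-vaccination if pre-vaccination neutralising antibody titre in" this range;
- above 8 and up to 10 log2 (256 to 1024): "At least a 2.5-fold increase from pre-vaccination if pre-vaccination neutralising antibody titre in" this range;
- above 10 log2 (1024): "At least 1-fold from pre-vaccination if pre-vaccination neutralising antibody titre" is above that value.

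Only the last line lacks the word *increase*. The section defers the handling of values below the quantification limit to the SAP, but fixes the response rule itself.

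Section 10.10 uses the rule among the within-group summaries: "Percentage of responders in terms of" neutralising antibody "titres will be tabulated with exact 95% CI", for each group and timepoint. The same section lists pre-vaccination categories above 10, 11 and 12 log2, so women are expected in the top tier. Section 1.2.3 gives placebo a role here: "The placebo group is included as a control for both the safety/reactogenicity and immunogenicity assessments".

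**The concern.** In the first three lines a k-fold increase is naturally a post/pre ratio of at least k. On the same reading, the fourth line asks for a ratio of at least 1, that is, no fall. Where the vaccine does nothing, measurement error and ordinary within-woman variation put many second readings at or above the first. Those women would be reported as vaccine responders.

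At stake is the meaning of the responder percentage. It would mix real boosting with noise in every group, placebo included, and the exact interval around it would describe that mixture precisely. A reader comparing a vaccine group with placebo would not see a near-zero background.

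**Working it through.** **Plan's own figures.** 2^7 = 128, 2^8 = 256 and 2^10 = 1024, as printed. The protocol states no placebo responder rate to reproduce.

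**Titre required on each side of a tier boundary** (baseline × required fold; no assumptions needed):

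| Boundary | Lower side | Upper side | Upper ÷ lower |
|---|---|---|---|
| 128 | 128 × 4 = 512 | 128 × 3 = 384 | 0.75 |
| 256 | 256 × 3 = 768 | 256 × 2.5 = 640 | 0.83 |
| 1024, as written | 1024 × 2.5 = 2560 | 1024 × 1 = 1024 | 0.40 |
| 1024, with 2-fold | 2560 | 1024 × 2 = 2048 | 0.80 |

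A rise from 1000 to 2400 is a 2.4-fold increase and fails; a flat 1100 passes.

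**Placebo responders in the top tier.** The inputs below are assumed because the protocol gives none of them:

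- baseline mean μ: 8 to 9.5 log2;
- between-woman SD σ: 1.0 to 1.5 log2;
- Day 0 to Day 30 correlation r: 0.7 to 0.98;
- no true change; log2 titres bivariate normal with equal means and SDs.

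For a woman with standardised baseline z = (x − μ)/σ, the chance that the second titre is at least the first is

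P = Φ(−z·√((1 − r)/(1 + r))).

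This is averaged over baselines above 10. Without regression to the mean it is 50%; regression to the mean lowers it. Putting in the mean z among women above 10 gives a close hand check on simulated values (1,000,000 draws per setting):

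| μ, σ, r | Share above 10 log2 | Mean z in tier | √((1−r)/(1+r)) | Hand check | Simulated |
|---|---|---|---|---|---|
| 8, 1.0, 0.7 | 2.3% | 2.373 | 0.420 | Φ(−0.997) = 15.9% | 16.1% |
| 9, 1.25, 0.9 | 21% | 1.367 | 0.229 | Φ(−0.314) = 37.7% | 37.9% |
| 9.5, 1.5, 0.98 | 37% | 1.021 | 0.101 | Φ(−0.103) = 45.9% | 46.0% |

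Range over the grid, by correlation: 16–34% at r = 0.7, 22–37% at 0.8, 30–41% at 0.9, 35–44% at 0.95, 41–46% at 0.98.

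**Effect on the whole placebo group.** In the middle setting, 0.211 × 0.379 = 8.0 points come from the top tier and 0.789 × 0.007 = 0.6 points from the rest. The total is about 8.5% after rounding, and about 94% of placebo responders come from the top tier. Over the grid, the top tier adds between 0.023 × 0.161 = 0.4 points and 0.369 × 0.460 = 17 points.

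**Sensitivity to drift in the middle setting.** A placebo change of −0.2 log2 lowers 38% to 25%; +0.1 log2 raises it to 45%.

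**Other top-tier thresholds on the same grid.** A 2-fold requirement gives about 0–9% placebo responders in the tier; carrying 2.5-fold upward gives about 0–5%.

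**The case against.** **It touches no listed endpoint or decision.** This stands. Vaccine response is absent from the endpoints in Sections 10.1 and 10.2. The desirability index (Section 10.8, Appendix E) uses baseline-adjusted Day 30 titres and concentrations plus adverse-event rates, and the sample-size simulations use the same quantities. A reader might infer that the formulation ranking is compromised; the documents do not support that.

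**Other outputs expose the problem.** Largely true. Section 10.10 also plans fold-increase distributions by pre-vaccination category, geometric mean ratios, and pre/post scatter plots with control as reference. Responder rates are already tabulated for the control group. This limits the harm but leaves the headline percentage as defined.

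**Every stepped rule jumps.** True, so the jump alone is not the defect. The defect is that the top step demands no rise.

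**High-baseline women are hard to boost.** This could justify a lower threshold. It does not justify counting no rise as a response, and the protocol offers no such rationale.

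**A doubling may have been meant.** Possible, and then the defect largely disappears. But reading 1-fold as a doubling while 4-fold means a ratio of 4 uses two conventions in one list, so the text needs clarifying either way.

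**The groups are randomised.** Allocation is to "four study groups in a (1: 1: 1: 1) ratio (approximately 100 subjects in each group", so the share of high-baseline women is balanced in expectation and the rule is the same in each group. A reader might infer that it favours one dose; nothing in the documents shows this. Minimisation uses age and centre, not baseline titre, so only chance imbalance remains.

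**Conclusion.** The defect is in the text: taken literally, the top tier makes non-decline a vaccine response. Its size is conditional. Under no true change, roughly 16% to 46% of placebo women above 10 log2 would be called responders, on the assumed means, SDs and correlations given above, with 50% as the ceiling absent upward drift or ties.

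A reader might state flatly that a third to nearly half of such women would qualify. That needs a correlation of about 0.9 or more (30–46%), or roughly a baseline mean of at least 9 log2 (27–46%). The protocol gives neither figure.

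The consequence is inflated descriptive responder percentages and a blurred comparison with placebo. The inflation in the vaccine groups was not computed, because it depends on the true rise in high-baseline women; how far the vaccine-placebo difference itself would move is therefore not established. The primary ranking and the sample size are unaffected. Severity is moderate or minor.

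**What to change.** In Section 10.6, reword the line for baselines above 10 log2 so that it requires a true increase, for example at least a 2-fold increase, which continues the 4, 3, 2.5 sequence. Apply it to both RSV-A and RSV-B. If a doubling was intended all along, write it as a post/pre ratio of at least 2. Carry the same wording into the SAP.

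The 2-fold figure is a choice. The documents give no assay precision, so it cannot be claimed to lie above assay noise, and Section 5.7.5 says there is no accepted correlate of protection to anchor it. If the sponsor prefers another threshold, a sentence of justification is enough.

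The cost is one line of text and a less favourable responder rate among high-baseline women. No new data, visits or subjects are needed.

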10.7. Analysis of demographics

The analysis of demography will be performed on the TVC and on the ATP cohort for immunogenicity.

Demographic characteristics (age at vaccination in years, race, ethnicity, vital signs and BMI) and cohort description will be summarised by group using descriptive statistics:

- Frequency tables will be generated for categorical variable such as race.
- Mean, median, standard error and range will be provided for continuous data such as age.

The distribution of subjects will be tabulated as a whole and per group and for each age category (18 - 32 years and 33 - 45 years).

Withdrawal status will be summarised by group using descriptive statistics:

- The number of subjects enrolled into the study as well as the number of subjects excluded from ATP analyses will be tabulated.
- The number of withdrawn subjects will be tabulated according to the reason for withdrawal.

10.8. Analysis for ranking RSV formulations

A desirability approach will be used to rank the formulations and guide the formulation selection, based on safety/reactogenicity and immunogenicity data up to 1 month post-vaccination.

This method is a multi-criteria decision making approach based on desirability functions. The main idea is to identify for each endpoint a desirability function that associates any value to another one between 0 and 1 depending on its desirability ('0' being considered as not desirable at all and '1' as the most desirable). An index with values between 0 and 1 will be created for each endpoint. An overall desirability index can be calculated by computing a weighted geometric mean of the endpoint indexes. By definition, this overall index also takes values between 0 and 1 and characterises the level of desirability of any candidate formulation by a single value [Dewé, 2015].

The desirability index calculations will include reactogenicity and safety data up to Day 7 post vaccination (on the TVC) and immunogenicity data at 30 days post-vaccination (on the ATP cohort for immunogenicity up to Day 30). The formulations will be ranked based on the values obtained with this overall desirability index. Refer to [APPENDIX E](#) for more details on the desirability analysis.

10.9. Analysis of safety

The analysis of safety will be performed on the TVC.

Within group evaluation

The percentage of subjects with at least one **local AE** (solicited and unsolicited), with at least one **general AE** (solicited and unsolicited) and with any AE during the 7-day or 30-day follow-up period after vaccination will be tabulated with exact 95% CI. The same computations will be done for \geq Grade 2 and Grade 3 AEs, for any AEs considered related to vaccination, for any Grade 3 AEs considered related to vaccination and for AEs resulting in medically attended visit.

The percentage of subjects reporting each individual **solicited local AE** (any grade, \geq Grade 2, Grade 3, resulting in medically attended visit) during the 7-day follow-up period after vaccination will be tabulated for each study vaccine for each group. The percentage of subjects reporting each individual **solicited general AE** (any grade, \geq Grade 2, Grade 3, any related, \geq Grade 2 related, Grade 3 related, resulting in medically attended visit) during the 7-day follow-up period after vaccination will be tabulated for each group.

For fever during the 7-day follow-up period after vaccination, the number and percentage of subjects reporting fever will be reported by half degree ($^{\circ}\text{C}$) cumulative increments. Similar tabulations will be performed for causally related fever, Grade 3 ($> 39.5^{\circ}\text{C}$) causally related fever and fever resulting in a medically attended visit. In addition, the prevalence of any and Grade 3 fever will be presented graphically over time after vaccination.

The percentage of subjects with any **unsolicited** symptoms within 30 days after vaccination with its exact 95% CI will be tabulated by group and by Medical Dictionary for Regulatory Activities (MedDRA) preferred term. Similar tabulation will be done for Grade 3 unsolicited symptoms, for any causally related unsolicited symptoms, for Grade 3 causally related unsolicited symptoms and for unsolicited symptoms resulting in a medically attended visit (The verbatim reports of unsolicited symptoms will be reviewed by a physician and the signs and symptoms will be coded according to the MedDRA Dictionary for Adverse Reaction Terminology. Every verbatim term will be matched with the appropriate Preferred Term).

SAEs reported throughout the study will be described in detail.

Pregnancy exposures throughout the study and pregnancy outcomes will be described in detail (if applicable).

The percentage of subjects using **concomitant medication** (any medication, any antipyretic and any antipyretic taken prophylactically) during the 7-day (Day 0 to Day 6) or 30-day (Day 0 to Day 29) follow-up period after vaccination will be summarised by group.

For all subjects in each group and each **haematology and biochemistry** parameter:

- The percentage of subjects having haematology and biochemistry results below or above the local laboratory normal ranges will be tabulated for each timepoint.
- The maximum grading post-vaccination (from Day 7 to Day 90) versus baseline (Day 0) and the percentage of subjects with laboratory parameters above or equal to Grade 1, Grade 2, Grade 3 and Grade 4 will be tabulated (Grades will be based on the FDA Guidance for Industry “Toxicity Grading Scale for Healthy Adult and Adolescent Volunteers Enrolled in Preventive Vaccine Clinical Trials”, see [APPENDIX D](#). Those laboratory parameters not included on FDA Toxicity Grading Scale will not be graded).

Assessment of anti-NEO immune response at Day 30 post-vaccination for each group:

- GMCs pre-and post-vaccination will be tabulated with 95% CI and represented graphically.
- Individual post-vaccination *versus* pre-vaccination results will be plotted using scatter plots. Results of the control group will be used as a reference.
- Geometric mean of ratios of antibody concentrations at Day 30 over pre-vaccination will be tabulated with 95% CI.
- Distribution of the antibody concentrations pre-and post-vaccination and of fold increase after vaccination will be tabulated.

Between group evaluation

Exploratory comparisons between each investigational RSV vaccine group and (minus) the control group (*placebo*), and between the RSV vaccine groups (PreF-120 *minus* PreF 30, PreF-120 *minus* PreF-60, PreF-60 *minus* PreF 30) will be done in terms of the

percentage of subjects reporting any \geq Grade 2, Grade 3 AE (solicited and unsolicited), and/or any fever $> 38.5^{\circ}\text{C}$, and/or any vaccine-related SAE during the 7-day follow-up period after vaccination.

The standardised asymptotic 95% CI for the difference between the investigational RSV vaccine groups as well as between the investigational RSV groups and (minus) the control group will be computed.

